Unless otherwise noted, all tests of treatment effects will be conducted at a 2-sided alpha level of 0.05, and CIs will be calculated at 95%, 2-sided. All tests of interactions between treatment groups and other factors will be conducted at a 2-sided alpha level of 0.10.

The definitions of baseline and postbaseline for the efficacy and safety analyses depend on which analysis period is being used. The following analysis periods will be used:

- Lead-in Period – Visits 2-8
- 26-Week Treatment Period – from randomization to Week 26 prior to discontinuation of IP and from randomization to Week 26 (including all data regardless of IP use) – all treatment groups
- 26-Week Treatment Period and Safety Follow-Up Visit – from randomization to Visit 801 (including all data regardless of IP) – LY900014+20 treatment group excluding patients from Japan
- 52-Week Treatment Period - from randomization to Week 52 prior to discontinuation of IP and from randomization to Week 52 (including all data regardless of IP use) – double-blind treatment groups
- 52-Week Treatment Period and Safety Follow-Up Visit – from randomization to Visit 801 (including all data regardless of IP use) – double-blind treatment groups.

Patients randomly assigned to the LY900014+20 treatment group in Japan will remain in the study until Week 52 and subsequently will have the Safety Follow-Up Visit only after Week 52 for patients who complete the study.

The data on IP is defined based on the following rules:

- for data only measured at an office visit
 - MMTT postbaseline data will be considered as data on IP if the MMTT performance date is on or prior to the last IP dose date
 - Other postbaseline data (for example, vital signs, laboratory tests, and questionnaires) will be considered as data on IP if the measurement date is on or prior to the cutoff date defined as 14 days after the last IP dose date
- for data collected as running records with an exact date stamp such as adverse events (AEs) and diary entries where the dates of the measures were not tied with the date of an office visit, postbaseline data with dates \leq (last study drug dose date +1) will be considered as data on IP.

Table 6.2 describes the rules for determining the patient population, baseline and postbaseline observations for the different analysis periods.

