TEAEs	Safety Population	Prior to first dose of randomized IP (or Visit 8 date if missing) and after the first dose of open-label insulin lispro (or Visit 2 date if missing)	From first dose of randomized IP to last dose of randomized IP AND From first dose of randomized IP to Visit 18 or from first dose of randomized IP to Visit 801 (for LY900014+20 treatment group)
Hypoglycemia events	Safety Population	All Visits 2-8	All Visits 9-18 prior to discontinuation of IP
Weight and vital signs	All Patients in the Safety Population with a baseline and a postbaseline observation	Last of Visits 2-8	Visits 9-18 prior to discontinuation of IP AND Visits 9-18 regardless of IP use or Visits 9-801 for LY900014+20 treatment group
Anti-insulin lispro antibody	Safety Population	Visit 2	Visits 3-18 AND Visits 3-801 (for LY900014+20 treatment group), regardless of IP use
52-Week Treatment Period (including Safety Follow-Up Visit where applicable)			
HbA1c	All Randomized Patients in the Double-Blind Treatment Groups	Last of Visits 7-8	Visits 11, 13, 15, 18, 20, and 22 prior to discontinuation of IP AND Last of Visits 9-22 prior to discontinuation of IP
10-point SMBG, basal, prandial, and total insulin doses, prandial/total insulin dose ratio	All Randomized Patients in the Double-Blind Treatment Groups	Visit 8 prior to initiation of IP	Visits 11, 13, 15, 18, 20, and 22 prior to discontinuation of IP AND Last of Visits 9-22 prior to discontinuation of IP
1,5-AG	All Randomized Patients in the Double-Blind Treatment Groups	Visit 8 prior to initiation of IP	Visits 11, 15, 18, 20, and 22 prior to discontinuation of IP AND Last of Visits 9-22 prior to discontinuation of IP
Health outcomes: ITSQ CCI	All Randomized Patients in the Double-Blind Treatment Groups	Last of Visits 1-8	Last of Visits 9-22 prior to discontinuation of IP
Safety Laboratory Tests (chemistry, hematology, lipids) – continuous analysis	All Double-Blind Patients in the Safety Population with a baseline and a postbaseline observation	Last of Visits 1-8	Visit 22 (planned) AND Last of Visits 9-22 (planned including early discontinuation), regardless of IP use

Baseline and Postbaseline Definitions and Patient Population by Study Period and Type of Analysis

Study Period/Analysis	Patient Population	Baseline Observations	Postbaseline Observations

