Safety Laboratory Tests (chemistry, hematology, lipids) – categorical analysis	All Double-Blind Patients in the Safety Population with a normal baseline (with respect to the direction being analyzed) and a postbaseline observation	Visits 1-8 (including unplanned tests)	Visits 9-22 (including unplanned tests) regardless of IP use.
TEAEs	All Double-Blind Patients in the Safety Population	Prior to first dose of randomized IP (or Visit 8 date if the dose date is missing) and after the first dose of open-label insulin lispro (or Visit 2 date if the dose date is missing)	From first dose of randomized IP to last dose of randomized IP AND From first dose of randomized IP to Visit 801
Hypoglycemia events	All Double-Blind Patients in the Safety Population	Visits 2-8	Visits 9-22 prior to discontinuation of IP
Weight and vital signs	All Double-Blind Patients in the Safety Population	Last of Visits 2-8	Visits 9-22 prior to discontinuation of IP AND Visits 9-801 regardless of IP use
Anti-insulin lispro antibody	All Double-Blind Patients in the Safety Population	Visit 2	Visits 3-801 regardless of IP use

Abbreviations: 1,5-AG = 1,5-Anhydroglucitol; ANCOVA = analysis of covariance; CCI [REDACTED]; HbA1c = hemoglobin A1c; IP = investigational product; ITSQ = Insulin Treatment Satisfaction Questionnaire; ITT = intention-to-treat; LOCF = last-observation-carried forward; MMTT = mixed meal tolerance test; MMRM = mixed-effect model repeated measures; SMBG = self-monitored blood glucose; TEAE = treatment-emergent adverse event CCI [REDACTED]

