6.12.7.1. Treatment Emergent Anti-Insulin Lispro Antibody

The treatment-emergent anti-insulin lispro antibody (denoted as treatment-emergent antidrug antibody [TEADA] throughout this SAP) is based on the change from baseline (Visit 2) to postbaseline (post-Visit 2) in the anti-insulin lispro antibody level (percent binding). Treatment-emergent antidrug antibody can be sub-classified as either treatment-induced (not detected anti-insulin lispro antibody at baseline) or treatment-boosted (detected anti-insulin antibody at baseline):

- treatment-induced response: change from not detected anti-insulin lispro at baseline (Visit 2) to postbaseline detected anti-insulin lispro;
- treatment-boosted response: change from detected anti-insulin lispro at baseline (Visit 2) to postbaseline detected anti-insulin lispro antibody level (percent binding) at least 157% of the baseline value.

The TEADA status during a specific analysis period will be determined using all data in the corresponding analysis period regardless of IP use. The summary for TEADA status and the anti-insulin lispro antibody level will use the same analysis data.

The number and percentage of patients with positive TEADA response during the treatment period of 0 to 26 weeks will be summarized by treatment group. For patients with positive TEADA response during the treatment period of 0 to 26 weeks, the number and percentage of patients with positive insulin cross-reactivity anytime during the treatment period of 0 to 26 weeks will also be summarized by treatment group. Treatment groups will be compared by Fisher's exact test.

The above summary of TEADA response will be repeated for the analysis period of Visit 2 to Visit 801. The 2 double-blind treatment groups and the open-label treatment group will be summarized separately due to different duration of treatment period. For patients with positive TEADA response, the number and percentage of patients not meeting the TEADA criteria at Visit 801 will also be summarized.

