Both actual and change from baseline (Visit 2) for the anti-insulin lispro antibody level in percent binding will be summarized by scheduled visit prespecified in the protocol for patients with positive TEADA response during the treatment period of 0 to 26 weeks. The repeated measurement from Visit 2 to Visit 18 will be analyzed by an MMRM model with treatment, baseline value of the response variable, visit, and visit by treatment interaction as fixed factors and patient as the random factor. The ANCOVA model using treatment and baseline value as covariates will be used for the analysis of maximum percent binding during the treatment period of 0 to 26 weeks. A similar summary of antibody level in percent binding during the analysis period of Visit 2 to Visit 801 will be generated separately for the 2 double-blind treatment groups and the open-label treatment group.

A listing of anti-insulin lispro antibody at each visit will be provided. The listing will include anti-insulin lispro antibody status (detected/not detected), anti-insulin lispro antibody percent binding, TEADA status (positive/negative), insulin cross-reactivity status, insulin cross-reactivity percent binding for the safety population.

Subgroup analysis for the following selected efficacy and safety variables will be performed by the TEADA status during the treatment period of 0 to 26 weeks:

- Use data prior to discontinuation of IP:
 - HbA1c and change from baseline in HbA1c
 - 1-hour and 2-hour PPG excursions
 - basal, prandial, and total insulin dose
 - event rate (per patient per year) of overall hypoglycemic events
- Use all data regardless of IP use:
 - treatment-emergent injection site reaction and hypersensitivity reaction

The analyses for HbA1c and change from baseline in HbA1c will be performed using an MMRM model for the primary analysis and the HbA1c data prior to discontinuation of IP. The model will include additional fixed terms of subgroup, subgroup by treatment interaction, subgroup by visit interaction, and 3-way interaction of treatment, subgroup, and visit.

The PPG excursions will be analyzed by the ANCOVA model same as the model specified in Section 6.11.2 using the efficacy estimand. The model will include additional terms of subgroup, subgroup by treatment interaction, subgroup by visit interaction, and 3-way interaction of treatment, subgroup, and visit.

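### The antibody post-baseline window includes the pre-randomisation Visit 8 sample, contrary to the SAP's own 0-to-26-week period, and the antibody MMRM uses Visit 2 as both response and covariate

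*SAP*

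**What the plan says.** SAP 6.1 states that Table 6.2 "describes the rules for determining the patient population, baseline and postbaseline observations for the different analysis periods". In that table the antibody baseline is Visit 2. The post-baseline window is "Visits 3-18 AND Visits 3-801 (for LY900014+20 treatment group), regardless of IP use" for the 26-week period and "Visits 3-801 regardless of IP use" for the 52-week period. SAP 6.12.7.1 repeats the rule: TEADA "is based on the change from baseline (Visit 2) to postbaseline (post-Visit 2) in the anti-insulin lispro antibody level (percent binding"). A boosted response needs a "postbaseline detected anti-insulin lispro antibody level (percent binding) at least 157% of the baseline value".

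Other text in the SAP sets different limits. Section 6.1 lists a separate "Lead-in Period – Visits 2-8" and starts the 26-week treatment period at randomisation. Section 6.12.7.1 determines TEADA status from the data in the corresponding analysis period and reports it over weeks 0 to 26, by arm, with Fisher's exact test.

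For the antibody level in TEADA-positive patients, 6.12.7.1 says: "The repeated measurement from Visit 2 to Visit 18 will be analyzed by an MMRM model". The model terms include the baseline value, which is the Visit 2 value.

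**The concern.** Objective 18 compares the incidence of treatment-emergent antibodies between arms. A response first seen at Visit 8 cannot have been caused by the randomised insulin, because randomisation follows all Visit 8 procedures (Protocol Section 2, footnote d) and every patient uses open-label lispro until then (Protocol 7.2.1.4). Under Table 6.2 such a response still counts in whichever arm the patient later enters. Randomisation balances these responses in expectation, so they pull the comparison toward no difference. In a safety comparison, that is the direction in which a real difference could be missed.

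The 0-to-26-week TEADA status also defines subgroups for HbA1c, PPG excursions, insulin dose, overall hypoglycemia, and injection site and hypersensitivity reactions, so the same attribution carries into those analyses. Two programmers could also build different TEADA flags from the same SAP.

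The MMRM is a separate matter. A model with Visit 2 among its responses and the Visit 2 value as a covariate regresses a measurement on itself.

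**Working it through.** The documents give no antibody rate, sample size or power, so there is no stated figure to reproduce.

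**1. Which samples fall in the window.** The antibody row of the Schedule of Activities (Protocol Section 2), read by column, has samples at Visits 2, 8, 10, 11, 15, 18, 22, 801 and early discontinuation. The window of Visits 3–18 therefore holds five scheduled samples (8, 10, 11, 15, 18). One of the five, Visit 8, precedes randomisation.

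**2. Comparison with the rest of Table 6.2.** In the 26-week block, the other safety rows place the lead-in in the baseline:
- adverse events: from first open-label lispro dose to first randomised dose;
- hypoglycemia: Visits 2–8;
- weight and vital signs: last of Visits 2–8;
- categorical laboratory tests: Visits 1–8, with post-baseline from Visit 9.

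Only the antibody row places the lead-in after baseline.

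**3. Size of the dilution.** Let L be the proportion already TEADA-positive at Visit 8, equal in expectation across arms. Let p0 and p1 be the rates of new response after randomisation among the rest. Then observed rate = L + (1 − L)p, and observed risk difference = (1 − L)(p1 − p0).

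Illustration with **assumed** p0 = 20% and p1 = 30%, 436 per arm (Protocol 10.1), two-sided 0.05, normal approximation:

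| L | Observed rates | Risk difference | Risk ratio | Power |
|---|---|---|---|---|
| 0% | 20.0 / 30.0% | 10.0 points | 1.50 | 92.8% |
| 1% | 20.8 / 30.7% | 9.9 | 1.48 | 91.8% |
| 5% | 24.0 / 33.5% | 9.5 | 1.40 | 87.4% |
| 10% | 28.0 / 37.0% | 9.0 | 1.32 | 81.1% |
| 20% | 36.0 / 44.0% | 8.0 | 1.22 | 67.5% |

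The factor (1 − L) does not depend on p0 and p1; the risk ratio and power do. At an assumed 10% vs 16%, L = 10% takes power from 75.1% to 49.0%; at 30% vs 40%, from 87.3% to 77.0%. The planned Fisher's test would have somewhat lower power throughout.

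**4. Dropping Visit 8 alone is not enough.** A lead-in response that persists to Visit 10 or later still counts against a Visit 2 baseline. With L = 20% and 80% of lead-in responses persisting (both assumed), the share counted whatever the arm is 0.20 × 0.80 = 16%. The observed rates are 0.16 + 0.84 × 0.20 = 32.8% and 0.16 + 0.84 × 0.30 = 41.2%, a difference of 8.4 points.

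**5. The MMRM.** At Visit 2 the response equals the covariate b. With a common baseline slope β = 1 − ε and free arm-by-visit means, the Visit 2 residual can be written ε(b − mean of b), with variance ε² × var(b). If Visit 2 has its own variance, that variance can shrink with ε. The log-likelihood then rises by N × ln 10 ≈ 2.30N for each tenfold reduction in ε, so it has no finite maximum. For change from baseline, the Visit 2 response is identically zero and the same happens as the slope approaches 0. Under an unstructured covariance the model is therefore degenerate, whatever L is. Under a structure with one pooled variance the model can be fitted, but the near-zero Visit 2 residuals can make the standard errors too small.

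**The case against.** **The Visit 2 baseline is deliberate.** SAP 6.12.7 explains that it precedes the first study-provided prandial insulin. The antigen, insulin lispro, is the same in the lead-in and in all three arms. The protocol uses Visit 2 throughout for follow-up eligibility, and the TEADA and return-to-baseline thresholds were to be agreed with the FDA (Protocol Appendix 8). This stands. A reader might infer that the TEADA definition is wrong and should be replaced; the documents do not support that. The definition suits cumulative response to study lispro. The difficulty is limited to its use for the between-arm comparison.

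**Competing text favours excluding Visit 8.** Section 6.1 starts the period at randomisation, 6.12.7.1 says weeks 0 to 26, and where the lead-in is wanted 6.12.7.1 names a separate period of Visit 2 to Visit 801. This also stands: it is not settled that Visit 8 will be counted in the 26-week comparison. What is established is the conflict with Table 6.2. Even on this reading, persistent lead-in responses remain in the count.

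**The size is assumed.** L may well be small. Patients had used insulin for at least a year and a rapid-acting analog for at least 90 days (Protocol 6.1), and only aspart or glulisine users changed analog at Visit 2. The power figures are illustrations only.

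**The MMRM wording may be loose.** Protocol 10.3.1 says MMRMs use post-baseline visits, so the phrase in 6.12.7.1 may describe the data span only. It should still be corrected. A reader might also compute standard errors about 9% too small, from 1 − √(5/6) with one of six visits contributing no residual. That needs a slope of exactly 1 and a pooled variance. The SAP fixes neither, so the figure should not be quoted as a finding.

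**Conclusion.** The concern holds in a limited form. Table 6.2 and 6.12.7.1 count everything after Visit 2 as post-baseline, which takes in a pre-randomisation sample, while 6.1 and other sentences of 6.12.7.1 describe a period that begins at randomisation. Under the Table 6.2 rule, the between-arm risk difference is multiplied by (1 − L). That is nothing of note if L is near zero, and a 5–20% relative shrinkage if L is 5–20%. The documents do not allow L to be estimated. The result rests on lead-in responses being balanced by randomisation and on the rates in step 3 being assumptions.

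The MMRM as written is degenerate under the protocol's default unstructured covariance and can misstate standard errors under simpler ones. It is confined to TEADA-positive patients.

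A reader might infer that the rule could create a false difference or inflate Type I error. It does neither: the effect is toward no difference, and under a true null it only raises the rates in every arm. Objective 18 is tertiary and outside multiplicity control. Primary and multiplicity-adjusted results are unaffected.

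**What to change.** - Keep the Visit 2-based TEADA definition and the 157% threshold for the cumulative summary and for antibody follow-up eligibility.
- Reconcile the antibody rows of Table 6.2 with the weeks 0-to-26 text, stating whether the Visit 8 sample counts.
- Report emergence from Visit 2 to Visit 8 separately, by randomised arm.
- Add a supplementary between-arm comparison using only samples after the first randomised dose (Visit 10 onward), with the Visit 8 value in the baseline. The risk difference then returns to p1 − p0 among patients without a lead-in response, or in all patients if lead-in responders carry the same later risk.
- Restrict the antibody MMRM responses to Visits 10, 11, 15 and 18.

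The cost is SAP wording, one extra derivation and one extra table; every sample is already scheduled. The drawback is that the supplementary analysis applies the 157% threshold to a baseline other than Visit 2, so patients already boosted in the lead-in face a higher bar. It should be labelled as supplementary for that reason.

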6.2. Adjustments for Covariates

Stratification factors of this study include country, HbA1c stratum ($\leq 7.5\%$, $>7.5\%$), type of basal insulin during the lead-in period (glargine or degludec), and prandial insulin dosing plan (carbohydrate counting, pattern adjustment). Stratification factors will be entered into the IWRS for randomization and also collected in the database by electronic case report form (eCRF) or central laboratory. The analysis models for efficacy endpoints will use the stratification factors as collected in the database.

For continuous analyses of HbA1c, the stratification factor of HbA1c stratum will not be included. Instead, the continuous value of baseline (Visit 8) HbA1c will be included in the analysis models.

For analyses of the incidence and rate of hypoglycemia, the baseline hypoglycemia event rate with the same category of the dependent variable will be included as a covariate in the analysis models.

Other analyses will include the stratification factors as noted in Sections 6.11 and 6.12.

6.3. Handling of Dropouts or Missing Data

The analyses for the primary and multiplicity adjusted objectives will be performed for the intention-to-treat (ITT) estimand including all data collected through Week 26 regardless of IP use and the efficacy estimand including data collected prior to discontinuation of IP through Week 26.

For the FDA submission, the ITT estimand will be used. For the analysis of HbA1c, imputation of missing data will be performed as described in Section 6.11.1.

For non-FDA submissions and publications, the efficacy estimand will be used. Missing data will be addressed by using a mixed-effect model repeated measures (MMRM) analysis for continuous longitudinal variables. The MMRM model provides consistent estimator when data is missing at random. The model implicitly adjusts for missing data through a variance-covariance structure. An ANCOVA model will also be used to analyze continuous variables. Unless otherwise stated, missing endpoints will be imputed using the last-observation-carried forward (LOCF) approach, using only postbaseline data, in the ANCOVA model.

6.4. Multicenter Studies

Countries in similar geographic regions with fewer than 10 patients, based on the Randomized Population, will be pooled to achieve a pooled country of at least 10 patients. Puerto Rico and the US are always pooled in the analysis, as Puerto Rico was considered part of the US during randomization. All analyses using country in the model will use a pooled country, unless otherwise specified. The final pooling by country and geographic region will be finalized prior to data lock.

Given the different treatment period length between the Japan patients (52 weeks) and non-Japan patients (26 weeks) in the open-label arm, at the primary objective database lock (up to Week 26 for patients in the double-blind arms and up to Visit 801 for the non-Japan patients in the open-label arm), all analyses of the open-label arm involving data from Visit 801 will not include Japan patients.

To support the registrations for Taiwan, Russia, Korea, Mexico, and India, a MEE Addendum was developed to allow patient enrollment to continue in the study for these countries if they do not meet their minimum enrollment requirements for local registration. Separate analyses for these countries will be conducted to support their local registration (Appendix 3).

6.5. Multiple Comparisons/Multiplicity

A graphical approach for multiple comparisons will be used to strongly control the overall Type I error (2-sided alpha level of 0.05) for testing the treatment effect for the primary and the

multiplicity adjusted objectives given in Section 4. See Section 6.11.2 for the details of graphical testing scheme.

No multiplicity test adjustment will be made for other objectives.

